## 7.2 Adverse Events

Adverse events (AE) will be collected starting at the time of informed consent until the End of Study visit on Week 12. An AE is defined as any untoward medical occurrence in a clinical trial subject. AEs will be analyzed for subjects in the SAF population. AEs will be coded using the Medical Dictionary for Regulatory Activities (MedDRA).

## 7.2.1 Treatment-emergent Adverse Events

Treatment-emergent adverse events (TEAEs) are defined as AEs starting during or after administration of the first dose of study drug. A determination of treatment emergence for AEs with missing or partial AE start dates and times will use a conservative approach that assumes treatment emergence when the true start time or date is unknown.

## 7.2.2 Adverse Event Severity

Severity describes the intensity of a specific adverse event. The Investigator will determine the severity of each AE according to the NCI CTCAE v5.0. AEs will be characterized as 'mild', 'moderate', 'severe', 'life-threatening', or 'death'.

## 7.2.3 Adverse Event Relationship to Study Medication

The Investigator will assign a relationship to each AE based on his/her determination of whether there exists a reasonable possibility that the IP caused or contributed to the AE. The AE relationship will be characterized as 'not related', 'unlikely related', 'possibly related', and 'definitely related'. For analysis purposes, AEs will be summarized by 'Related' (including 'possibly related' and 'definitely related') and 'Not Related ('unlikely related' and 'not related'). AEs with missing relationship will be considered to be 'Related' events.

## 7.2.4 Serious Adverse Events

A serious adverse event (SAE) is defined as an AE that meets at least one of the following criteria:

- Results in death
- Is life-threatening
- Requires hospitalization or prolongation of existing hospitalization
- Results in a disability/incapacity
- Congenital anomaly/birth defect
- Other medically important serious event

## 7.2.5 Adverse Events of Special Interest

Adverse events of special interest (AESI) are defined as a subset of AEs that are suggestive of abuse potential and any special situations defined in Section 9.9 of the protocol that have an associated AE. The following MedDRA Preferred Terms will be used to classify AESIs related to abuse liability:

• Euphoria-related terms: Euphoric mood; Elevated mood; Feeling abnormal; Feeling drunk; Feeling of relaxation; Dizziness; Thinking abnormal; Hallucination; Inappropriate

affect.

- Terms indicative of impaired attention, cognition, and mood: Somnolence; Mood disorders and disturbances.
- Dissociative/psychotic terms: Psychosis; Aggression; Confusion and disorientation.
- Overdose- / Misuse-related terms not captured elsewhere: Drug tolerance; Habituation; Drug withdrawal syndrome; Substance-related disorders.

#### 7.2.6 Adverse Event Summaries

AEs (serious and non-serious) occurring after completion of the informed consent process and before the end of study, regardless of relationship to study drug, will be included and classified by system organ class (SOC) and preferred term (PT) using the Medical Dictionary for Regulatory Activities (MedDRA).

For treatment-emergent AEs (TEAEs) occurring during the entirety of the study, the following will be summarized and presented for the SAF set:

- i. An overall summary of TEAEs, which includes:
  - a. the number and percentage of subjects experiencing a TEAE
  - b. the number and percentage of subjects experiencing a TEAE by strongest relationship to study drug
  - c. the number and percentage of subjects experiencing a TEAE by greatest severity
  - d. the number and percentage of subjects experiencing a TEAE with NCI CTCAE grade 3 or higher
  - e. the number and percentage of subjects experiencing a treatment emergent SAE (TESAE)
  - f. the number and percentage of subjects experiencing a treatment emergent AESI
  - g. the number and percentage of subjects experiencing a TEAE leading to study withdrawal
  - h. the number and percentage of subjects experiencing a TEAE leading to death
- ii. the number and percentage of subjects experiencing a TEAE by SOC and PT
- iii. the number and percentage of subjects experiencing a TEAE by PT in overall descending order
- iv. the number and percentage of subjects experiencing a TEAE by SOC, PT and the highest severity
- v. the number and percentage of subjects experiencing a TEAE by SOC, PT and the strongest relationship to study drug
- vi. the number and percentage of subjects experiencing a TESAE by SOC and PT
- vii. the number and percentage of subjects experiencing a TESAE by PT in overall descending order
- viii. the number and percentage of subjects experiencing a TESAE by strongest relationship to study drug

- ix. the number and percentage of subjects experiencing a TEAE leading to study withdrawal by SOC and PT
- x. the number and percentage of subjects experiencing a TEAE leading to study death by SOC and PT
- xi. the number and percentage of subjects experiencing a treatment emergent AESI by SOC and PT

Additionally, two tables, the incidence by severity of TEAE by SOC and PT (ii), and the incidence by severity of TESAE by SOC and PT (vi), will also be presented separately for AEs starting on Study Day 1 (dosing day) and for those AEs starting post Study Day 1. For AEs starting on Day 1 (dosing day) the duration, in days, will be summarized by descriptive statistics.

In the overall summary of TEAEs table (i), besides tabulating the number and percentage of subjects, the total number of TEAE episodes will also be provided. If a subject has repeated episodes of a particular TEAE, all episodes will be counted in the summary table.

In the remaining summary tables, the incidence of TEAEs will be calculated by dividing the number of subjects who have experienced the event by the total number of subjects in the Safety Analysis set. Thus, the incidence of TEAEs is shown in terms of the total number of subjects and not in terms of the total number of episodes. If a subject has repeated episodes of a particular TEAE, only the most severe episode, or the episode with the strongest causal relationship to study drug, will be counted in the summary tables.

A subject with more than one type of TEAE in a particular SOC will be counted only once in the total of subjects experiencing TEAEs in that particular SOC. Since a subject could have more than one type of TEAE within a particular SOC, the sum of subjects experiencing different TEAEs within the SOC could appear larger than the total number of subjects experiencing TEAEs in that SOC. Similarly, a subject who has experienced a TEAE in more than one SOC will be counted only once in the total number of subjects experiencing AEs in all SOCs.

All occurrences of all AEs will be listed for each subject, grouped by treatment group. The listing will contain the following information: treatment group, verbatim term, SOC, PT, severity, relationship to study medication, date and day of onset, date and day of resolution, action taken, the outcome, and whether the event was an SAE. Listings will be sorted by subject identification number, onset date, SOC, and PT. If the onset date is completely missing, then these events will be presented first. If the onset date is missing a month or a day, then these events will be presented before any complete dates. Additional listings of SAEs, AEs leading to Study Withdrawal, and Subject Deaths will be provided.

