9.4. Adverse Event Detecting and Reporting

The Investigator and site staff are responsible for detecting, documenting and reporting events that meet the definition of an AE, SAE or AESI suggestive of abuse potential.

The reporting of SAE and/or AESIs suggestive of abuse potential to regulatory authorities by the Sponsor is a requirement and each authority has a timetable for reporting these events based upon established criteria. Likewise, it is the responsibility of the Investigator to report SAE and/or AESIs suggestive of abuse potential to their local IRB/IEC.

Care will be taken not to introduce bias when detecting AEs, SAEs and/or AESIs suggestive of abuse potential. Open-ended and non-leading verbal questioning of the subject is the preferred method to inquire about adverse event occurrence. Appropriate questions include:

- "How are you feeling?"
- "Have you had any (other) medical problems since your last visit/contact?"
- "Have you taken any new medicines since your last visit/contact?

Any abnormal exam finding(s) at Screening and Baseline should be entered once as medical history and as a physical exam finding (if applicable). The finding will only be considered an AE if there is a clinically significant change in signs or symptoms during the study, as judged by the Investigator. A medical history finding that worsens after randomization should be recorded as an AE. The term should match the recorded finding that has worsened.

The subject's responses in clinician reported outcome measures will not be used as a primary means to collect AEs, however any AEs indicated in these instruments should be queried by the study site personnel and the study monitors and recorded. Should the Investigator or site staff become aware of a potential AE through the information collected with these instruments, proper follow-up with the subject for medical evaluation should be undertaken. Through this follow-up, if it is determined that an AE not previously reported has been identified, normal reporting requirements should be applied.

All subjects who experience an AE will be evaluated at appropriate time intervals until the event resolves or has stabilized or become chronic. At the conclusion of the study, the Investigator and medical monitor will assess unresolved AEs and determine if additional follow-up is warranted.

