## 4.5 Handling of Dropouts or Missing Data

Missing data on demographics, baseline information and safety measures will be treated as missing; no imputation is planned.

Missing or partial dates and times will be imputed for analysis purposes in a manner that imputes the most conservative date or time. Imputation methods for dates and times are described for each endpoint where applicable.

Details of missing data imputation will be specified in the analysis methods for the primary and key secondary efficacy endpoints. Subject-completed questionnaires will be considered missing if incomplete. Missing data will not be imputed for analysis of non-key secondary efficacy endpoints or safety endpoints.

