## 4.7 Data Derivations and Transformations

The following derivations will be used in this study:

Study Day:

- Equal to (date of assessment date of first dose + 1) for assessments done on or after date of first dose
- Equal to (date of assessment date of first dose) for assessments before date of first dose

Baseline Observation: the last non-missing value prior to first study drug administration.

Duration: end date – start date +1; measured in days.

Change from Baseline: post-baseline value - baseline value

Percent Change from Baseline: (post-baseline value - baseline value) / baseline value x 100

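### SAP 7.2.6 has no rule for adverse events still ongoing at last contact, so the Day 1 duration summary may be biased downward and no summary table shows persistence

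*SAP*

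**What the plan says.** **Split tables.** SAP 7.2.6 takes two tables, TEAEs and serious TEAEs by SOC, PT and severity, and says that they "will also be presented separately for AEs starting on Study Day 1 (dosing day) and for those AEs starting post Study Day 1". The criterion is the day of onset.

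**Duration.** The same section adds: "For AEs starting on Day 1 (dosing day) the duration, in days, will be summarized by descriptive statistics". SAP 4.7 defines duration as "end date – start date +1; measured in days".

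**Missing values.** SAP 4.5 contains three relevant statements:
- On safety data: "Missing data on demographics, baseline information and safety measures will be treated as missing; no imputation is planned". It repeats this later: "Missing data will not be imputed for analysis of non-key secondary efficacy endpoints or safety endpoints".
- On dates: "Missing or partial dates and times will be imputed for analysis purposes in a manner that imputes the most conservative date or time".
- On where the date methods are given: "Imputation methods for dates and times are described for each endpoint where applicable". For adverse events, the only such method is in SAP 7.2.1. It concerns start dates and serves to decide treatment emergence.

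**Unresolved events are foreseen.** Protocol 9.4 has events followed until they resolve, stabilise or become chronic, and says: "At the conclusion of the study, the Investigator and medical monitor will assess unresolved AEs". Protocol 9.4.2 likewise provides for serious events and AESIs that continue past study completion.

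**Addendum.** SAP addendum 4.1.2 adds tables of TEAEs 'occurring' on and after the dosing day, without defining the word. Addendum section 1 says that the pre-planned analyses are unchanged.

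**The concern.** Whether the effects of a single dose outlast the dosing day is a main safety question here. Protocol 2.3 describes adverse reactions at doses up to 200 µg as typically mild and gone within a day, and SAP 5.8 refers to both acute and lasting effects. The Day 1 duration summary is the planned statistic that bears most directly on this.

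An event that has not ended has no end date, so the SAP 4.7 formula returns nothing for it unless a date is supplied. If the programmer leaves it missing, the statistics describe resolved events only. Those left out are the ones followed to last contact without resolving, so the mean and maximum move in one direction, towards short duration.

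The split tables do not make up for this. They place an event by its onset, so one that begins on Day 1 and is still present at Week 12 is counted among dosing-day events and not among later ones.

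**Working it through.** The plan states no figure on this point, so there is none to reproduce. The check follows one event through the rules and then illustrates the size.

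**1. One event through the rules.** Take an event that starts on Day 1 and is ongoing at the Week 12 visit (target Day 85, window ±5 days, so Day 80 to 90).
- Split tables (SAP 7.2.6): counted in the Day 1 table if it meets the table's definition, and not counted in the post-Day 1 table.
- Whole-study tables i to xi (SAP 7.2.6): counted, with no indication of timing or resolution. This includes the AESI table.
- AE listing (SAP 7.2.6): resolution date and outcome are shown for that subject, but there is no rate by arm.
- Duration (SAP 4.7): not calculable without an end or censoring date. Taken to the visit, it is 85 − 1 + 1 = 85 days (range 80 to 90), which is a lower bound.

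**2. Which SAP 4.5 sentence governs?** One reading leaves the duration missing, because safety measures are not imputed. The other supplies a conservative end date, because absent dates are imputed. The second reading lacks a method: SAP 4.5 defers to endpoint-specific descriptions, and none exists for an AE end date. SAP 5.7, by contrast, gives an end-date rule for medications (latest possible day or month) and mentions medications ongoing at completion. It is also unclear that an end which has not yet happened counts as a missing date. Two programmers could follow the SAP and produce different summaries.

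**3. Illustrative size.** Assumptions, none from the documents: one arm has 36 Day 1-onset events, k are ongoing at End of Study, and the rest end on Day 1 (duration 1 − 1 + 1 = 1 day).

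Mean with ongoing events omitted = (36 − k) × 1 / (36 − k) = 1.00 day for any k.

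Mean with ongoing events counted to Day D = [(36 − k) × 1 + k × D] / 36.

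| k ongoing | Omitted: mean / max | Counted to Day 85: mean (Day 80 to 90) / max | Median, either way |
|---|---|---|---|
| 1 | 1.00 / 1 | (35 + 85)/36 = 3.33 (3.19 to 3.47) / 85 | 1 |
| 2 | 1.00 / 1 | (34 + 170)/36 = 5.67 (5.39 to 5.94) / 85 | 1 |
| 4 | 1.00 / 1 | (32 + 340)/36 = 10.33 (9.78 to 10.89) / 85 | 1 |

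With 20 events and k = 2, the mean is (18 + 170)/20 = 9.40 days (8.90 to 9.90) against 1.00.

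If the k events fall in k different subjects of a 36-subject arm (SAP 9), then 1/36 = 2.8%, 2/36 = 5.6% or 4/36 = 11.1% of the arm has a persisting event. These events add nothing to the post-Day 1 table.

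The means counted to Day D are lower bounds, because the ongoing events had not ended. The median does not move in any of these cases, so reporting it would not reveal the problem.

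**The case against.** **The SAP does not say that ongoing events are excluded.** A reader might infer a planned exclusion of the longest events. The documents do not support that. The general date sentence in SAP 4.5 could supply a conservative end date, and the medication rule in SAP 5.7 suggests what that might be. The defect is an unspecified and conflicting rule. This part of the objection stands.

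**Persisting harm is not simply reported as a dosing-day event.** A reader might infer that too, and it goes too far. The split applies to two additional tables, openly defined by onset. The whole-study tables count every event without a day label. The listing gives resolution date and outcome, and arms of about 36 make it reviewable. The neuropsychiatric examination is listed by visit (SAP 5.8), and C-SSRS is tabulated at each scheduled time point (SAP 7.7). Protocol 10.2.3.1 plans summaries, listings or narratives for serious events and AESIs as appropriate. The addendum's tables of events 'occurring' after the dosing day may include carried-over events. All of this stands, but none of these outputs is a by-arm summary of Day 1-onset events that persist, and the addendum's term is undefined.

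**The example is constructed.** This is also fair. The counts are invented, and the maximum of 1 day arises only because every other event is assumed to end on Day 1. An event that lasts weeks and then resolves has a valid duration and enters the summary.

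**The number of non-missing observations will be printed (SAP 4), so omissions would be visible.** Only in part. The split tables count subjects, and episodes are totalled only in the whole-study overview. No planned summary gives the number of Day 1-onset episodes against which that n could be compared.

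**Conclusion.** The point holds as a gap in specification with a predictable direction of error. SAP 7.2.6 plans plain descriptive statistics on a quantity that is undefined for ongoing events, and SAP 4.5 does not settle what to do with them. If they are omitted, the mean and maximum duration are biased downward. If they are instead given last contact as an end date with no flag, a lower bound is presented as an observed duration. Under either reading, no planned summary table shows by arm how many Day 1-onset events persisted.

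The size is unknown, because the documents give no expected number of ongoing events. The 5.67 against 1.00 day comparison rests wholly on the assumed 36 events with 2 ongoing at Day 85. If every Day 1 event resolves before last contact, the duration statistics are unaffected, though the onset-only split still hides events that ran past Day 1.

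The output is descriptive and carries no hypothesis test (SAP 7), so the efficacy conclusions are not touched. The correction is still worth making, because the affected statistic bears on a main safety question and the remedy is cheap.

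**What to change.** In SAP 7.2.6:
1. State that Day 1-onset events ongoing at last contact are censored there, for example with a Kaplan-Meier summary of time to resolution. State that this rule takes precedence over SAP 4.5 for AE end dates.
2. Print the number of events ongoing beside the duration statistics. This is the minimum that makes those statistics interpretable.
3. Add one by-arm table of Day 1-onset TEAEs and AESIs still ongoing after Day 1 and at last contact.

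In addendum 4.1.2, say whether an event carried over from Day 1 counts as 'occurring' after the dosing day.

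The cost is a few sentences of SAP text and one or two extra descriptive tables. Resolution date and outcome are already planned for the AE listing, so no new data are needed. The change concerns reporting only and alters no clinical rule.

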2.3. Dose Rationale

Based on literature review, LSD has been safely administered in over 1000 subjects in studies with various levels of control and at doses up to $800~\mu g$, including more than 200 subjects across 12 trials conducted since 2008. To date, however, full interrogation of the dose-response curve for LSD has not been established, and no prior dose-finding study has been completed for MM-120. The doses of 25, 50, 100 and 200 μg MM-120 (freebase-equivalent) used in the current study have been selected based on preliminary evidence of safety and clinical effect from prior, published studies of LSD. Dose increases from 100 μg to 200 μg have been associated with an increase in "bad drug effect" while not resulting in increased "overall or good drug effect" (Holze 2021a), but doses within this range (and above) have been demonstrated to be safe.

The minimal recognizable ("threshold") dose of LSD in humans (i.e., the dose at which psychoactive effects are perceivable by patients on average) is reported to be approximately 10-25 µg (Bershad 2019; Holze 2021b; Hutten 2020) and doses above 50-75 µg typically produce an altered state of consciousness (including enhanced capacity for introspection, altered psychological functioning and perceptual changes such as illusions, pseudo-hallucinations, synesthesia and alterations of thinking and time experience) (Holze, 2020; Holze 2021a; Passie 2008). Under supportive supervised conditions (i.e., appropriate set and setting) and at doses up to 200 µg LSD freebase-equivalent, adverse drug reactions were typically mild and resolved within a day. Transient anxiety, short-lived headaches, nausea and mild increases in heart rate and blood pressure were the most commonly reported adverse events (AEs).

The 4 individual dose levels of MM-120 in the current study have been selected to assess both: 1) the dose-response relationship over a wide dose range that has been previously shown to be safe in clinical trials; and 2) the functional mechanism of action, specifically the extent to which psychedelic effects mediate clinical outcomes. The rationale for each dose level is provided in Table 3.

Table 3: Rationale for Selected MM-120 Doses

Dose of MM-120 (μg) (Freebase-equivalent)	Rationale
0	Placebo control – an inactive placebo is the most appropriate control for the Multiple Comparison Procedure-Modelling (MCP-Mod) statistical approach to be used in the current study and for characterization of dose-response

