8.6.4. Subject Release on Dosing Day/ Dosing Release Checklist

Study subjects will be kept under continuous observation for a minimum of 12 hours following investigational drug administration.

Beginning approximately 8 hours after drug administration, the Dosing Release Checklist will be performed by the site-designated licensed physician (MD/DO) to evaluate the subject's psychological and physiological status. This will include an evaluation to ascertain that the subject no longer meets DSM-5 criteria for Hallucinogen Intoxication. Subjects should be assessed for release criteria starting at 8 hours (±10 minutes) post-administration and subsequently assessed at approximately 9, 10, 11 and 12 hours (±10 minutes) post-dose. The Dosing Session Release Checklist should be administered hourly (±10 minutes) until all release criteria are met. At a minimum, the Dosing Release Checklist will be completed at 8- and 12-hours post-dose. If the subject does not meet criteria for release at 12 hours post-dose, the Dosing Session Release Checklist should be repeated approximately every hour (±10 minutes) until all criteria are met and the subject is deemed eligible for release. Subjects will be kept under continuous observation until their release is deemed safe by the site-designated licensed physician.

In order to be eligible for release, subjects MUST:

• Self-report readiness for release (i.e., physical and mental readiness, and understanding of restrictions); and

Clinical Study Protocol: MMED008

• Be deemed eligible for safe release in the medical judgment of the study sitedesignated licensed physician as determined by the Dosing Release Checklist

No active suicidal ideation or behavior as determined by the C-SSRS

And must NOT:

- Meet DSM-5 criteria for Hallucinogen Intoxication
- Display clinically significant psychomotor depression, activation or other signs or symptoms
- Display clinically significant abnormal mental status

Refer to the Dosing Session Monitor Manual and Dosing Release Checklist for further details on requirements that must be met in order for the subject to be released from the clinic at the end of Day 1/Dosing Session (Visit 3B).

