11.10.6. Study Files and Retention of Records

The Investigator must maintain adequate and accurate records to enable the conduct of the study to be fully documented and the study data to be subsequently verified. These documents should be classified into at least the following two categories:

- 1. Investigator's study file. The Investigator's study file will contain the Investigator's Brochure, protocol/amendments, IRB/IEC and governmental approval with correspondence, informed consent forms, drug records, staff curriculum vitae, authorization and training forms and other appropriate documents and correspondence.
- 2. Subject clinical source documents. The required source data should include the following for each subject:
 - Subject identification (name, date of birth, gender)
 - Documentation that the subject meets eligibility criteria (e.g., history, physical examination, and confirmation of diagnosis to support inclusion and exclusion criteria)
 - Participation in the study (including study number)
 - Study discussed and date of informed consent
 - Dates of all visits
 - Documentation that protocol-specific procedures were performed
 - Results of efficacy parameters, as required by the protocol
 - Dosing date of study drug
 - Record of all adverse events and other safety parameters (start and end date, and causality and intensity as assigned by the Investigator)
 - Concomitant medication (including start and end date)

• Date of study completion and reason for early discontinuation, if applicable.

All clinical study documentation must be retained by the Investigator until at least 2 years after the last approval of a marketing application in an ICH region (i.e., United States, Europe, or Japan) and until there are no pending or contemplated marketing applications in an ICH region; or, if no application is filed or if the application is not approved for such indication, until 2 years after the investigation is discontinued and regulatory authorities have been notified. Investigators may be required to retain documents longer if required by applicable regulatory requirements, by local regulations or by an agreement with the Sponsor. The Investigator must notify the Sponsor before destroying any clinical study records.

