## 4.1.1 Treatment-emergent Adverse Events

Treatment-emergent adverse events (TEAEs) are defined as AEs starting during or after administration of the first dose of study drug. A determination of treatment emergence for AEs

with missing or partial AE start dates and times will use a conservative approach that assumes treatment emergence when the true start time or date is unknown.

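### Duration of dosing-day AEs is counted in whole calendar days, so every AE that resolves on the dosing date scores 1 day whatever its length

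*SAP*

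**What the plan says.** SAP 7.2.6 separates AEs that start on the dosing day from those that start later. For the first group it adds: "For AEs starting on Day 1 (dosing day) the duration, in days, will be summarized by descriptive statistics". That section gives no derivation of its own. The general derivation in SAP 4.7 defines duration as "end date – start date +1; measured in days".

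On the timing data behind this:

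- The AE listing in SAP 7.2.6 carries "date and day of onset, date and day of resolution, action taken, the outcome, and whether the event was an SAE". It has no clock time.
- Protocol 11.10.6 asks for this in the source documents: "Record of all adverse events and other safety parameters (start and end date, and causality and intensity as assigned by the Investigator". It mentions dates only.
- Clock times for AEs appear only in the rule for treatment emergence. SAP 7.2.1 refers to "AEs with missing or partial AE start dates and times", and section 4.1.1 of the SAP Addendum repeats this.

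On the time scale of the effects, Protocol 2.3 reports that under supervised conditions, at doses up to 200 µg, "adverse drug reactions were typically mild and resolved within a day". Protocol 8.6.4 states: "Study subjects will be kept under continuous observation for a minimum of 12 hours following investigational drug administration".

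**The concern.** This is a single-dose trial of a drug whose acute effects are expected to run over hours. The SAP picks out dosing-day AEs for a duration summary, and its safety section presents summaries by treatment group. SAP 6.1.2 makes the final choice of target dose depend partly on safety considerations. A reader of the study report would expect this table to show whether acute AEs last longer at higher doses.

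A date-based count cannot show that for events that begin and end on the same date, because they all receive the same value. It can also put events in the wrong order, since a short event that straddles midnight outranks one that filled most of the session. The SAP Addendum adds dosing-day and post-dosing-day incidence tables by severity and relationship, but no further duration measure.

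**Working it through.** The plan gives no figure to reproduce. The check applies its own rule to example events.

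**Inputs.** The rule is from SAP 4.7: D = end date − start date + 1. The minimum observation time of 12 hours is from Protocol 8.6.4. The documents give no dosing clock time, so all clock times below are assumptions.

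**Step 1: apply the rule.**

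| AE starting on Day 1 | Date difference + 1 | SAP duration | Elapsed time |
|---|---|---|---|
| 10:00 to 10:10 | 0 + 1 | 1 day | 0.17 h |
| 10:00 to 11:00 | 0 + 1 | 1 day | 1.0 h |
| 09:30 to 21:00 | 0 + 1 | 1 day | 11.5 h |
| 23:45 to 00:15 next date | 1 + 1 | 2 days | 0.5 h |
| 09:30 to 08:30 next date | 1 + 1 | 2 days | 23.0 h |

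The first three events differ widely in length and score the same. The fourth lasts 0.5 h and scores higher than the third, which lasts 11.5 h.

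**Step 2: dependence on dosing time.** Take an AE that spans the full 12 hours after dosing. Checked at whole hours, dosing at 07:00 to 11:00 gives 1 day and dosing at 12:00 to 15:00 gives 2 days. The same 12-hour event changes value with the clock time of dosing.

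**Step 3: what the summary can show.** Let p be the proportion of Day 1 AEs in an arm that resolve on the dosing date, and suppose for simplicity that the rest resolve on the next date. The mean duration is then 1 × p + 2 × (1 − p) = 2 − p. The median is 1 whenever p exceeds one half, and the upper quartile is 1 whenever p exceeds three quarters. In that setting the mean only restates p, and the median and quartiles can be identical across arms whatever happens to duration in hours. The documents give no value of p. Protocol 2.3 suggests that it is high, but resolution within a day can still mean resolution on the next calendar date.

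**Step 4: can hours be derived?** Hours need both a start and a stop time. SAP 7.2.1 implies that start times exist. No section of either document mentions AE stop times, and Protocol 11.10.6 and the AE listing name dates only.

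**The case against.** The strongest reply is that days answer a sensible question. Once dosing-day AEs are separated from later ones, a duration of 1 shows that the event ended that date, and a larger value shows that it persisted. Given the expectation in Protocol 2.3, persistence beyond the dosing date is of real interest. The table is descriptive, and SAP 7 plans no formal testing of safety. This stands, and it limits the point to a loss of detail. It does not justify a mean or median in days, because a proportion would answer the persistence question more directly.

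Three stronger readings are tempting, and the documents do not support them.

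- A reader might infer that nothing else planned shows how long acute effects last or bears on the length of monitoring. SAP 5.9 summarises the number and percentage of subjects who meet release criteria at each hourly check. Under Protocol 8.6.4 those criteria cover hallucinogen intoxication, psychomotor signs and mental status, checked from 8 hours. Vital signs are taken from 0.5 to 12 hours post-dose (Protocol 8.2.3) and summarised at each scheduled measurement (SAP 7.4). Neither gives the duration of an AE, and the release checks do not resolve effects that end before 8 hours, but both are informative.
- A reader might infer that exact durations are collected and then discarded. Only start times are mentioned, so this is not established.
- A reader might convert 1 day to 24 hours and quote an overstatement factor. The SAP reports a count of calendar dates under a stated rule, not elapsed hours. Any such factor would depend entirely on the event length chosen.

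**Conclusion.** The point holds as a minor one. Read together, SAP 7.2.6 and SAP 4.7 fix the duration of every AE that resolves on the dosing date at 1 day, and they give 2 days to even a brief event that crosses midnight. This follows from the definition and needs no assumption.

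How much contrast between doses is lost depends on the share of Day 1 AEs that resolve on the dosing date, which the documents do not give. If most do, as Protocol 2.3 makes plausible, the median will be 1 in every arm, and the remaining contrast will come only from events that run past midnight. The primary and key secondary analyses, alpha and power are untouched.

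**What to change.** In SAP 4.7 and 7.2.6:

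1. Summarise the duration of Day 1-onset AEs by arm in hours, from start and stop date-time, where both are recorded.
2. Use days when either time is missing, and state how many events that concerns.
3. Give the number of events still ongoing at release from the dosing session.

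Before adopting this, confirm that the AE eCRF page has a stop-time field for dosing-day AEs, or add one. If stop times cannot be had, replace the mean and median in days with the proportion of Day 1 AEs that resolve on the dosing date, by arm. That needs only dates.

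The cost is one derivation if stop times already exist, or an eCRF field if they do not. For subjects already dosed, a new field would have to be filled from source notes. Some events will lack a stop time and stay in days, so the table will mix two units and should show the count in each.
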